## **6.0 Response Measures**

### **6.1 Safety Measures**

Adverse events, including serious adverse events, reoperations and revisions, up to 60 months

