## 10.7 Efficacy

### 10.7.1 Primary Endpoint Analysis

The primary endpoint analysis is described above in section 10.5. Statistical power for testing the primary efficacy hypothesis was approximated as follows. In the FAS, the mean

A Post Approval Multicenter Open-label

Randomized Controlled Trial of Agili-C™ vs.

Surgical Standard of Care (SSOC) for the  
Treatment of Joint Surface Lesions of the Knee

CLN0021-US

Rev. 8

March 29, 2022

(SD, N) improvement was 43.0 (20.1, N=160) and 20.5 (20.9, N=79) among subjects treated with Agili-C and SSOC, respectively, or a group difference of 22.5. Since this is a 5-year study, for the purpose of sample size justification, it was assumed that the sample sizes would be 75% as large, or 120 and 59, respectively. It was further assumed that the SD would be 20% higher than the maximum of 20.1 and 20.9 or 25. Under these assumptions, statistical power based on a pooled t-test with 1-sided type 1 error rate of  $\alpha=0.025$ , is 99%. If the mean improvement at 5 years is only 80% as large as observed at Month 24 for Agili-C, i.e., 34.4, or a group difference of only 13.9, then statistical power is 93.5%. Under these assumptions, as long as the group difference in mean improvements from baseline to Month 60 is at least as large as 11.2, then power is at least 80%. Further, these computations are conservative since the statistical modelling will include information for subjects up to the point of loss-to-follow-up. Therefore, statistical power appears adequate for confirming Month 60 superiority given the results from Month 24 and reasonably conservative assumptions.

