## **10.8 Safety**

Safety analyses will be conducted on the safety analysis set. All AEs, including all SAEs and device/procedure related events (including possibly and probably related), will be summarized and tabulated. In addition, the following will be monitored:

- Secondary surgery rate
- Conversion to major knee procedure, such total/partial knee arthroplasty (TKA) and osteotomies
- Overall Failure Rate

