4.4 Safety Endpoint

Adverse events, including serious adverse events, reoperations and revisions, up to 24 months.

5 Treatment Failure Definition

- For both Agili-C™ & SSOC groups: any secondary invasive treatment in the treated joint, regardless if related or unrelated to the original treatment, will be considered a treatment failure. Invasive interventions include: open procedure, mini-open procedure, arthroscopic procedure and intra articular injections, such as: HA, PRP, stem cells and steroids.
- Additionally, for the Agili-C™ arm: failure to implant the device in indicated patients will be considered a treatment failure. However, failure to implant the device in contraindicated patients/conditions will not be considered a treatment failure.

6 Randomization

Subjects will be randomized to either receive the Agili-C™ device or the control arm SSOC in a 2:1 ratio. Subjects will be randomized by site using variable block sizes of 3 and 6.

7 Interim Analyses

Details for the interim analyses, decision criteria, models, imputation procedures, simulations and operating characteristics for the design are included in the Adaptive Design Report attached as Appendix 1. The interim analyses will be conducted by an independent statistician and reviewed by the Endpoint Adjudication Committee (EAC).

The interim analyses, as described in Appendix 1, include only the primary endpoint - change from baseline to 24 months in average overall KOOS score. For the EAC review, we will also summarize and test the first confirmatory secondary endpoint - change from baseline to 24 months in KOOS Pain subscore, using a Bayesian posterior probability of superiority. For this secondary confirmatory endpoint, the interim analysis will NOT include a longitudinal model to multiply impute incomplete observations. However, similarly to the primary outcome, we will consider any treatment failures to have the change from baseline to 24 months Pain subscore replaced with their baseline value. At the earlier interim analyses, there may be only a few

subjects that have reached 24-months of follow-up. If fewer than 30 subjects have completed follow-up at an interim analysis, no testing of the first confirmatory secondary endpoint will be performed and only descriptive statistics will be provided to the EAC.

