9.6 Safety Analyses

Safety analyses will be conducted on the safety analysis set and will include all AEs, SAEs and USADEs.

The following summaries will be provided:

- An overall summary of the number and percentage of patients and AEs by SOC (System Organ Class) and PT (Preferred Term).
- An overall summary of the number and percentage of patients and events of SAEs by SOC and PT
- An overall summary of the number and percentage of patients and events of USAEDs by SOC and PT
- An overall summary of the number and percentage of patients and events of AEs by SOC, PT and Severity.
- An overall summary of the number and percentage of patients and events of AEs by SOC, PT and Outcome.

Anticipated AEs, listed in the eCRF, will be described by their pre-specified terms as collected in the eCRF. AEs which are not pre-specified in the eCRF will be coded and aggregated using MedDRA (Medical Dictionary for Regulatory Activities) version 18.2.

The AEs will be summarized with frequency and percentage of total subjects and number of events, and will be summarized and presented by treatment group.

For the summaries of AEs, subjects who experience the same AE more than once will only be counted once for that event in the number of subjects, but all occurrences of the same event will be counted in the number of events.

The AEs related to the implant, the tool-set and the procedure will be summarized with frequency and percentage of total subjects and number of events by these categories and by their pre-specified terms as collected in the eCRF, when applicable.

9.6.1 *Treatment Failure Rate*

The Treatment Failure Rate will be summarized with the number and percentage of subjects experienced Treatment Failures (section 5.0). The percentages between arms will be compared with a two-sided Chi Square test with significance alpha = 0.05

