9.9 Subject Disposition

The patient disposition will be summarized as follows and presented for each treatment group, when applicable, and overall. The percentages will be calculated based on the number of randomized patients, unless otherwise specified.

- The number (%) of patients who started screening process but were not enrolled (failed screening before enrollment) - % calculated from the all enrolled subjects, including the distribution of the reasons for failing the screening
- The number of enrolled patients
- The number (%) of patients randomized to the study (% calculated from the all enrolled subjects)
- The number (%) of patients with treatment or procedure failure (% calculated from the randomized subjects)
- The number (%) of patients in the different analysis sets (Safety, FAS and PP sets, (% calculated from the randomized subjects)
- The number (%) of patients who completed the study (% calculated from the randomized subjects)
- The number (%) of patients who discontinued the study prematurely including the distribution of reasons for premature discontinuations (% calculated from the randomized subjects)
- The number (%) of patients by visit (% calculated from the randomized subjects)

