10.4 Other Analyses

Additional secondary and safety data will not be subject to any imputation and will be summarized on an observed case basis.

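### The 60-month treatment failure and secondary surgery rates have no stated estimator; carrying forward the 24-month SAP's crude percentage would understate each arm's rate under the planned loss to follow-up.

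*SAP*

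**What the plan says.** SAP 9.6.1 summarises treatment failure as the number and percentage of subjects, and then: "The percentages between arms will be compared with a two-sided Chi Square test with significance alpha = 0.05". SAP 9.9 also reports failure under disposition and fixes the base there: "The number (%) of patients with treatment or procedure failure (% calculated from the randomized subjects"). SAP 10.4 says of safety data: "Additional secondary and safety data will not be subject to any imputation and will be summarized on an observed case basis".

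That SAP is the 24-month pivotal plan. Its safety endpoint (4.4) is "Adverse events, including serious adverse events, reoperations and revisions, up to 24 months". The post-approval protocol moves the horizon (6.1): "Adverse events, including serious adverse events, reoperations and revisions, up to 60 months". Protocol 10.8 then lists, as items to be monitored, the secondary surgery rate, conversion to a major knee procedure and "Overall Failure Rate". It gives no estimator, denominator, time point or test for any of them.

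Neither document contains a time-to-event method or a censoring rule. On loss, Protocol 10.7.1 says "it was assumed that the sample sizes would be 75% as large, or 120 and 59, respectively".

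**The concern.** Failure and reoperation are central long-term safety results for an implant, and Protocol 11.0 has safety results posted publicly after each interim report. Over five years, some subjects will leave before they have either failed or reached Month 60. A simple percentage of randomised or treated subjects keeps such a subject in the denominator as a non-failure. Someone lost at Month 30 is thus counted as failure-free through Month 60.

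If an analyst fills the gap in Protocol 10.8 with the only method available, SAP 9.6.1, the reported 60-month rates will be too low in both arms. If loss also differs between the arms, which is plausible in an open-label trial, the comparison itself can be biased.

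**Working it through.** **The plan's own figures.** The documents give no power and no 60-month rate for failure, so the usable figure is the loss assumption in Protocol 10.7.1: 0.75 × 160 = 120 and 0.75 × 79 = 59.25, taken as 59, i.e. 25% loss. With those sizes, SD 25 and a pooled t-test at one-sided 0.025, the stated KOOS power reproduces: 93.5% at 13.9 points (stated 93.5%) and 80.0% at 11.2 (stated at least 80%). The inputs are therefore read as intended.

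**Assumptions that are not document figures.** These are the 60-month failure rates, constant hazards, loss independent of failure, and the split of loss by arm. Arms and losses are given in the order Agili-C, SSOC.

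**Loss spread over 60 months.** Let F be the true 60-month failure probability, L the probability of loss if failure does not come first, a = −ln(1−F) and b = −ln(1−L). The expected crude proportion is

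a/(a+b) × [1 − e^−(a+b)].

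- F = 15%, L = 25%: a = 0.1625, b = 0.2877; 0.3610 × (1 − 0.85 × 0.75) = 0.131.
- F = 35%, L = 25%: a = 0.4308, b = 0.2877; 0.5996 × (1 − 0.65 × 0.75) = 0.307.

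So 15% reads as 13.1% (12.8% of its value too low) and 35% as 30.7% (12.2% too low). The difference reads as 17.6 points instead of 20.

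**Loss only in months 24 to 60.** The first 40% of follow-up has no loss, so the expected crude proportion is

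1 − e^(−0.4a) + e^(−0.4a) × a/(a + b/0.6) × [1 − e^−(0.6a+b)].

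- F = 15%: 0.0629 + 0.9371 × 0.0809 = 0.139.
- F = 35%: 0.1583 + 0.8417 × 0.1992 = 0.326.

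The rates are 7.5% and 6.9% of their value too low, and the difference is 18.7 points.

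**Unequal loss, spread over 60 months.**

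| True rates | Loss | Crude rates | Crude difference | True difference |
|---|---|---|---|---|
| 15%, 35% | 15%, 35% | 13.9%, 28.9% | 15.0 | 20 |
| 15%, 35% | 35%, 15% | 12.3%, 32.5% | 20.2 | 20 |
| 20%, 30% | 15%, 35% | 18.5%, 24.7% | 6.2 | 10 |
| 20%, 30% | 35%, 15% | 16.4%, 27.8% | 11.4 | 10 |

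**Type I error.** The SAP's planning failure rate (Section 8) is 15% per arm. Taken as a 24-month rate and extended at constant hazard, it gives 1 − 0.85^2.5 = 33.4% at 60 months. With that rate in both arms and 4,000 simulated trials of 167:84 (251 split 2:1), rejection at two-sided 5% was:

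| Loss | Chi-square | Log-rank |
|---|---|---|
| 25%, 25% | 5.1% | 5.0% |
| 20%, 35% | 6.9% | 4.9% |
| 15%, 45% | 13.8% | 5.3% |

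**Power.** With true rates of 15% and 30%, chi-square against log-rank power was 72% against 74% (25% loss in each arm), 61% against 74% (20%, 35%) and 46% against 72% (15%, 45%). With 35%, 20% it was 82% against 73%. Kaplan-Meier averaged within 0.2 points of the truth in all of these.

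**The other denominator.** If the observed-case wording in SAP 10.4 were read as failures plus completers only, the bias would reverse. With 25% loss, 15% reads as 0.131/(0.131 + 0.85 × 0.75) = 17.0%, and 35% as 0.307/(0.307 + 0.65 × 0.75) = 38.7%.

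**The case against.** **The test is not prescribed for five years.** A reader might infer that the plan compares five-year failure by chi-square. The documents do not say so. The test sits in a SAP whose safety endpoint ends at 24 months, and the reuse of pivotal models in Protocol 10.5 concerns the primary KOOS analysis. This stands: the 60-month method is absent, not wrongly chosen.

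**The 25% is a KOOS planning figure.** It is applied to the full analysis set behind the Month 24 result, so loss probably falls mainly after Month 24. This stands too and makes the smaller understatement, about 7%, the more likely of the two.

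**The comparison may be sound.** A reader might infer that crude percentages always distort the difference. They do not. Equal loss attenuates it modestly and leaves the chi-square type I error near 5%. Heavier loss in the lower-failure arm can leave the difference almost unchanged or enlarge it. No document figure says how loss splits by arm.

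**Some of this is covered elsewhere.** Protocol 10.6.1 and 10.6.2 require dropout effects to be assessed, disposition by arm and visit, and a dropout list with times. Unequal loss will therefore be visible, but seeing it does not correct the rates. Subjects whose routine visits end after index-knee surgery (Protocol 7.3.8 and 7.3.9) already count as failures and add no bias to the failure rate.

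**Kaplan-Meier is no cure for informative loss.** This is correct, and it is why a sensitivity analysis is needed.

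**Conclusion.** The point holds as a gap with a predictable consequence. Protocol 10.8 names 60-month failure and secondary surgery rates without a method, and the one method available, SAP 9.6.1 with the SAP 9.9 denominator, would understate each arm's rate. Under the assumed true rates of 15% and 35% with constant hazards and 25% loss, the understatement is about 12-13% of the rate if loss is spread over 60 months, and about 7% if it falls after Month 24. In points, 15% would read as 13.1% or 13.9%, and 35% as 30.7% or 32.6%.

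Material distortion of the between-arm comparison is conditional on unequal loss, with its direction set by which arm loses more. The denominator is also not fully settled between SAP 9.9 and 10.4. Failure lies outside the confirmatory hierarchy, so neither the primary KOOS test nor trial success is affected. The change is still worth making before the 60-month report, because absolute failure rates are a main output of long-term device follow-up.

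**What to change.** For the 60-month report, add to the protocol or a 60-month SAP:

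- Define time from procedure to first treatment failure, and separately to first secondary surgery. State the analysis set, and censor at last contact. Treat death as a competing event, or censor it with a justification.
- Report Kaplan-Meier (or cumulative incidence) estimates at 24 and 60 months by arm with 95% intervals, and an interval for the difference.
- Compare arms with a log-rank test stratified by K/L stratum. Keep crude counts as a descriptive table with the denominator stated.
- Report loss by arm and time, and add a sensitivity analysis for informative loss, since Kaplan-Meier and log-rank assume non-informative censoring.

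The dates needed are already collected: event dates under Protocol 9.3 and discontinuation times under 10.6.2. The cost is a little programming and slightly wider intervals.

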9.7 Covariate Analyses

Covariate analyses will be done on the PP population for the primary and secondary confirmatory endpoints by including each covariate of interest in an MMRM model, for both treatment groups, with one MMRM model per covariate listed below. Each covariate will appear in one MMRM.

The covariates are

- Age
- Gender
- BMI
- Lesion type (chondral or osteochondral)
- Number of lesions (single or multiple)
- Level of osteoarthritis (K/L score 0-1 or 2-3)
- Lesion size (total lesion size $\leq 3\text{cm}^2$ or $>3\text{cm}^2$)
- Previous ligament reconstruction (with or without)
- Meniscus status (intact, previous partial meniscectomy, concomitant meniscectomy)
- Activity status (active or inactive)

Note that the effect of interest is the Treatment x Covariate interaction term in the MMRM model, which will be tested using a 0.15 significance level.

Additionally, descriptive statistics will be provided by covariate level for categorical covariates.

For categorical covariates, we will perform an additional analysis, similar to the primary analysis, within each category of the covariate. From this analysis, the credible interval for the treatment effect will be reported for each category and assessed overlap.

9.8 Demographic and Baseline Characteristics

Demographics and baseline characteristics will be summarized descriptively for the PP, FAS and Safety sets, by treatment group and overall.

- Demographics: age (continuous and categorized), gender (categorical), ethnicity (categorical) and race (categorical)
- Baseline Characteristics include the following:
 - Body Weight Index (BMI)
 - Lesion type (chondral or osteochondral)
 - Number of lesions (single or multiple)
 - Level of osteoarthritis (K/L score 0-1 or 2-3)
 - Lesion size (total lesion size $\leq 3\text{cm}^2$ or $> 3\text{cm}^2$)
 - Previous ligament reconstruction (with or without)
 - Meniscus status (intact, previous partial meniscectomy, concomitant meniscectomy)
 - Activity status (active or inactive)

9.9 Subject Disposition

The patient disposition will be summarized as follows and presented for each treatment group, when applicable, and overall. The percentages will be calculated based on the number of randomized patients, unless otherwise specified.

- The number (%) of patients who started screening process but were not enrolled (failed screening before enrollment) - % calculated from the all enrolled subjects, including the distribution of the reasons for failing the screening
- The number of enrolled patients
- The number (%) of patients randomized to the study (% calculated from the all enrolled subjects)
- The number (%) of patients with treatment or procedure failure (% calculated from the randomized subjects)
- The number (%) of patients in the different analysis sets (Safety, FAS and PP sets, (% calculated from the randomized subjects)
- The number (%) of patients who completed the study (% calculated from the randomized subjects)
- The number (%) of patients who discontinued the study prematurely including the distribution of reasons for premature discontinuations (% calculated from the randomized subjects)
- The number (%) of patients by visit (% calculated from the randomized subjects)

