## A Post Approval Multicenter Open-label

## Randomized Controlled Trial of Agili-C™ vs.

Surgical Standard of Care (SSOC) for the  
Treatment of Joint Surface Lesions of the Knee

CLN0021-US

Rev. 8

March 29, 2022

Methods:	
 
• Candidates will be evaluated by the investigator based on an MRI (NMT one year old), X-ray (AP and Lateral; NMT one year old), clinical history and physical examination
 
• Prior to Screening, the candidate will sign and date the ICF using the IRB/EC approved form in accordance with local regulations
 
• Following signing of the informed consent, subjects will undergo Initial Screening using study questionnaires.
 
• The investigator will send the MRI and X-ray (AP and Lateral) for off-site evaluation. The X-ray will be evaluated by an independent radiologist, in order to determine the level of osteoarthritis according to Kellgren-Lawrence grade.
 
• In cases of K/L <4 and absence of clear exclusion criteria on MRI (as determined off-site), subjects will undergo Final Screening via Arthroscopy, not more than 90 days after Initial Screening. Arthroscopic findings will verify the subject's eligibility for study enrollment, and if found eligible will be Enrolled into the study and Randomized intra-operatively into either Agili-C™ or SSOC
 
• During the course of the procedure, mechanical-symptom generating lesions will be managed (such as synovectomy, loose body removal and partial meniscectomy) 
 
○ Agili-C™: Agili-C™ implantations will be performed via an arthrotomy or mini-arthrotomy procedure, using a designated surgical toolset
 
○ SSOC: microfracture and/or debridement procedures will be performed arthroscopically according to standard practice
 
 
 
• Ligamentoplasty is not allowed concomitantly
 

----------	--

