## 7.2 Subject Entry Procedures

### 7.2.1 Informed Consent Form and Subject Privacy

The purpose, procedures, risks, benefits, and alternatives to study participation will be discussed with each potential subject who has a knee surface lesion. Prior to any study-related procedures, the subject must sign an IRB/EC approved ICF and HIPPA Form (if applicable). If any new relevant information becomes available, the Sponsor will provide an updated ICF and HIPAA forms for IRB review and approval. The subject should personally sign and date the ICF and HIPAA forms. Upon signing the Informed Consent Form and authorization forms, the subject is considered to be a consenting individual in the study and receives a Subject Number that will be used on all documentation for the subject throughout the study.

After signing the Informed Consent Form, the consenting individual can then proceed with the screening evaluation. Surgery (Visit 2) must be performed within 1-90 days of signing the Informed Consent Form. During this period, if the subject decides to withdraw consent, the subject will then be considered as a screen failure. This will be captured in the screening log as well as in the CRF End/Exit form.

 CartiHeal	CLN0021-US-Investigational Plan A Post Approval Multicenter Open-label Randomized Controlled Trial of Agili-C™ vs. Surgical Standard of Care (SSOC) for the Treatment of Joint Surface Lesions of the Knee	Document Number: CLN-0000002 Document Version: 8.0 Effective Date: 08-Jun-2022 (GMT+2) Page 28 of 80
		CLN0021-US Rev. 8 March 29, 2022

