### **7.3.2 Final Screening/Procedure Visit (Visit 2)**

- Between 1 to 90 days after initial screening, subjects will undergo Final Screening (Visit 2) via arthroscopy. If found eligible, the subject will be enrolled into the study and randomized intra-operatively into either Agili-C™ or SSOC. Stratification will be performed based on K/L score performed off-site.
- For the SSOC group, lesion treatment will be determined according to subject's age, lesion size and K/L grade (Table 1) as per the control group selection algorithm (Figure 3).

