**Arthroscopy Procedure**

The arthroscopy procedure will be conducted according to hospital practice. Once subjects have fulfilled all the inclusion and none of the exclusion criteria, they will be enrolled into the study and randomized. The arthroscopy procedure should be video recorded according to hospital practice and documented post-procedure by the PI or study team on the relevant CRF assessment forms. The following structures should be carefully assessed by visualization and palpation:

- Synovia
- Patellar surface
- Trochlea surface
- Medial and lateral condylar surface

A Post Approval Multicenter Open-label

Randomized Controlled Trial of Agili-C™ vs.

Surgical Standard of Care (SSOC) for the  
Treatment of Joint Surface Lesions of the Knee

CLN0021-US

Rev. 8

March 29, 2022

- Medial and lateral tibial surface
- Medial and lateral meniscus
- Cruciate ligaments

Additionally, each lesion, regardless if symptomatic or not and if treated or not, should be documented according to the following parameters: location, severity (ICRS grade) and size (maximum length and maximum width). A company representative will be allowed to participate in the arthroscopy and to film the implantation procedure.

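### SAP 9.9 divides screen failures by enrolled subjects, a group that contains none of them, so the row reports a ratio that overstates the screen-failure proportion

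*SAP*

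**What the plan says.** SAP 9.9 sets a default for the disposition table: "The percentages will be calculated based on the number of randomized patients, unless otherwise specified". The first row overrides it with the words "failed screening before enrollment) - % calculated from the all enrolled subjects". In full, that row counts "patients who started screening process but were not enrolled (failed screening before enrollment"), and its percentage is to be "calculated from the all enrolled subjects, including the distribution of the reasons for failing the screening". The next rows give the number enrolled and the number randomised, the latter also as a percentage of those enrolled. No row gives the number screened, and no percentage uses it.

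The SAP does not define enrolment, but the Protocol does so consistently in three places:

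- Synopsis (Section 2.0), Methods: arthroscopy verifies eligibility, and subjects "if found eligible will be Enrolled into the study and Randomized intra-operatively".
- Section 7.3.2: "If found eligible, the subject will be enrolled into the study and randomized intra-operatively into either Agili-C™ or SSOC".
- Arthroscopy Procedure, within the Visit 2 description: "Once subjects have fulfilled all the inclusion and none of the exclusion criteria, they will be enrolled into the study and randomized".

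Signing consent is an earlier and different step. Under Protocol 7.2.1, on signing, "the subject is considered to be a consenting individual in the study and receives a Subject Number". The same section treats a subject who withdraws consent before surgery as a screen failure.

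**The concern.** A percentage of subjects who failed screening should be taken from the subjects who were screened. Here the numerator and denominator are mutually exclusive groups, so the result is not a proportion of anything. It would nevertheless sit in the table labelled as a percentage and would naturally be read as the screen-failure rate.

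What is at stake is modest. Candidates pass an off-site review of X-ray and MRI and then an arthroscopic check before randomisation. The screen-failure row is where a reader looks to see how many were turned away. As written, the percentage in that row is too high whenever there is at least one failure.

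**Working it through.** **Inputs**

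- S = number who started screening but were not enrolled. Not given in either document, so assumed over a range.
- E = number enrolled. Taken as 251 for illustration, from Protocol 5.10 (up to 251 subjects enrolled in the pivotal study).
- Neither document states a screen-failure rate, so there is no plan figure to reproduce.

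**Step 1: do the two groups overlap?** The row's own wording places its patients outside enrolment. The three Protocol statements place enrolment after eligibility is confirmed. The overlap is zero on either basis.

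**Step 2: formulas**

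- SAP rule: S/E.
- Proportion of those screened: p = S/(S+E).
- Overstatement factor: (S/E) ÷ (S/(S+E)) = (S+E)/E = 1/(1-p).

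**Step 3: numbers, with E = 251**

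| Assumed S | SAP rule S/E | Proportion S/(S+E) | Factor |
|---|---|---|---|
| 28 | 28/251 = 11.2% | 28/279 = 10.0% | 1.11 |
| 63 | 63/251 = 25.1% | 63/314 = 20.1% | 1.25 |
| 100 | 100/251 = 39.8% | 100/351 = 28.5% | 1.40 |
| 167 | 167/251 = 66.5% | 167/418 = 40.0% | 1.67 |
| 251 | 251/251 = 100.0% | 251/502 = 50.0% | 2.00 |

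**Step 4: dependence on E.** The factor depends only on p. Repeating the calculation with E = 250 or 500, the limits of the sample-size range in SAP 1.1, gives the same factors at the same p, apart from rounding of S.

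**Step 5: could a looser meaning of enrolled rescue the rule?** If the SAP used the word to mean consented or screened, the denominator would be S+E and the percentage would be correct. But the same row says that these patients were not enrolled and failed before enrolment. The word would then need two meanings within one row, and a pre-surgery withdrawal would count both as enrolled and as a screen failure. The text does not support that reading, and if it were the intention the wording would still need changing.

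**The case against.** The strongest reply is that nothing is hidden. The table must show the number of screen failures, their reasons and the number enrolled, so S/(S+E) can be worked out from it. No endpoint, analysis set, test or error rate uses the percentage. This stands, and it limits the weight of the point. It does not make the stated rule correct.

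A second reply is that the SAP governs the 24-month pivotal phase, whereas the Protocol follows subjects already enrolled and itself reports 24-month results in Section 10.7.1. This also stands: the correction matters only for a pivotal disposition table that is still to be issued, or is reissued or carried into later reports.

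A third is that the SAP never defines enrolment and may have meant consent. The percentage randomised among those enrolled hints at this, since under the Protocol it should be close to 100%. The row's own wording rules it out, as shown in the check.

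A reader might also infer more than the documents support:

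- **That the reported rate will exceed 100%.** This needs more failures than enrolled subjects, meaning that over half of those screened failed. With the number screened not given, it is only an arithmetical possibility.
- **That the percentage randomised is also wrong.** It is not. The Visit 2 activity list has final enrolment and randomisation as separate steps, so randomised over enrolled is a valid proportion, and a value near 100% is what one would expect.
- **That Protocol 10.6.2 repeats the error.** It has no screen-failure row and names no denominator.
- **That the row misstates how well the randomised knees represent the indicated population.** The off-site grading removes Kellgren-Lawrence grade 4, which the indication excludes anyway. The reasons for failure, which are reported, carry more of that information than the overall percentage.

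**Conclusion.** The rule in SAP 9.9 is wrong as written. It produces the odds of screen failure and presents them as a percentage, overstating the proportion by 1/(1-p): about 11% in relative terms if one in ten fails screening, and double if half do. The direction of the error is certain for any S above zero. Its actual size cannot be determined, because it depends on a screening count that the documents do not give. The conclusion rests on the Protocol's meaning of enrolment, which the SAP row's own wording supports.

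This is a minor point about one descriptive percentage. It has no bearing on the superiority test, the confirmatory endpoints, the analysis populations or the safety summaries.

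**What to change.** In SAP 9.9, add a first row for the number of subjects who started screening, defined as those who signed consent and received a Subject Number. Use that number as the denominator for the screen-failure percentage. State separately which denominator applies to the distribution of reasons: all who started screening, or all screen failures. If a pivotal disposition table has already been produced under the present rule, a footnote giving the denominator and the recalculated percentage would be enough.

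Reporting failures before arthroscopy separately from those found ineligible during it would be informative, but is optional. The row for the percentage randomised and Protocol 10.6.2 can stay as they are.

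The cost is a line or two of SAP text and one table row, with no new data collection expected. Protocol 7.2.1 sends pre-surgery withdrawals to the screening log and the CRF exit form. Section 7.7 has the investigator record why consented subjects did not reach randomisation, and Section 17.0 keeps a site list of those not enrolled, with reasons.
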